8.1 Imorphics MRI Assessments

The analyses of the imorphics MRI will be made on the ITT group and on the PPS population.

The observed values and the derived change from baseline values will be listed and summarized descriptively for the following MRI variables:

- MRI of the bone area of the medial femur for the target knee.
- MRI of the cartilage thickness for the target knee.
 - CM_FEMUR_THCTAB: Average thickness of cartilage in the central medial femur region
 - CM_TIBIA_THCTAB: Average thickness of cartilage in the central medial tibia region
- MRI of the total bone marrow lesion volume for the target knee

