8.1.1 Statistical Analysis – Imorphics MRI Assessments

A linear mixed effects model will be used to assess the behaviour of the MRI response over the entire period of the two studies, i.e. from visit 2 in study MIV-711-201 to visit 5 in study MIV-711-202. The model will include fixed factors for study group (A or B), visit, group*visit interaction, baseline analgesic user (Yes/No), and random effect for site and patient.

Patients considered analgesic users at baseline will be identified via concomitant medication analgesic usage. A patient exposed to a prescribed analgesic and ongoing medication at time of the first 200 mg MIV-711 intake (visit 2 study MIV-711-201 for patients in group A and visit 2 study MIV-711-202 for group B) will be considered as a baseline analgesic user.

The dependent variable in the linear mixed model is the observed MRI score. Separate mixed model analyses will be considered for each of the MRI endpoints noted in section 8.1. The following SAS code will be used as default, but a reduced model may be used in case of convergence issues:

```
PROC MIXED data=;  
  CLASS patient visit group baseline_conmed_pain_use;
```

PAREXEL International Statistical Analysis Plan

Medivir
Protocol: MIV-711-202

Final 1.0
16 January 2018

```
MODEL MRI_score = group visit group*visit baseline_conmed_pain_use/ DDFM=KR ;  
RANDOM site;  
REPEATED visit / SUBJECT=patient TYPE=UN;  
LSMEAN group*visit / diff CL ALPHA=0.1 ;  
RUN;
```

In case of convergence issues, a reduced model will be used to achieve convergence. The first two model reductions that will be considered are the following:

1. Simplify the covariance structure by using a compound symmetry covariance structure instead of unstructured.
2. Omit the random effect of site

The mean level and the change from visit 2 in study MIV-711-201 will be estimated for each population*visit combination in the model above together with the corresponding 90% confidence interval. The estimates and confidence intervals will be tabulated and visualized over visits with the two groups in the same table/figure (see example figures and example table below). In this example table and example figures (Figure 1, Figure 2 and Table 1), 'Population A' and 'Population B' refer to Group A and Group B.

PAREXEL International Statistical Analysis Plan

Medivir
Protocol: MIV-711-202

Final 1.0
16 January 2018

Figure 1 Example figure of estimated mean levels

[figure not shown]
[figure not shown]

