Figure 2 Example figure of estimated change from visit 2 (MIV-711-201)

PAREXEL International Statistical Analysis Plan

Medivir
Protocol: MIV-711-202

Final 1.0
16 January 2018

Table 1 Example table of statistical analysis corresponding to Figure 1 and Figure 2.

Endpoint	Population	Visit	N	Estimated Mean level		Estimated Change from Visit 2, Study MIV-711-201	
				LS Mean	95% CI	LS Mean Difference from V2 MIV-711-201	
						95% CI	95% CI
MRI of Bone Area Medial femur region	A	V2:201	nn	xx	(xx, xx)		
		V8:201	nn	xx	(xx, xx)	xx	(xx, xx)
		V5:202	nn	xx	(xx, xx)	xx	(xx, xx)
	B	V2:201	nn	xx	(xx, xx)		
V8:201		nn	xx	(xx, xx)	xx	(xx, xx)	
V5:202		nn	xx	(xx, xx)	xx	(xx, xx)	

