Table 14.3.1.6	Number and Percentage of Patients with Treatment Emergent Adverse Events by Frequency, Preferred Term, and Group
Table 14.3.2.1	Clinical Laboratory Chemistry Summary of Observed Values, SAF Population
Table 14.3.2.2	Clinical Laboratory Hematology Summary of Observed Values, SAF Population
Table 14.3.2.3	Clinical Laboratory Chemistry – Shift From Baseline to Maximum Value, SAF Population
Table 14.3.2.4	Clinical Laboratory Chemistry – Shift From Baseline to Minimum Value, SAF Population
Table 14.3.2.5	Clinical Laboratory Hematology – Shift From Baseline to Maximum Value, SAF Population
Table 14.3.2.6	Clinical Laboratory Hematology – Shift From Baseline to Minimum Value, SAF Population
Table 14.3.3	Vital Signs Blood Pressure and Heart Rate Summary of Observed and Change from Baseline Values, SAF Population
Table 14.3.4.1	12 Lead ECG – Summary of Observed and Change from Baseline Values SAF Population
Table 14.3.4.2	12-Lead ECG – Categorical Summary of Observed Values, SAF Population
Table 14.3.4.3	12-Lead ECG – Categorical Summary of Change From Baseline, SAF Population

PAREXEL International Statistical Analysis Plan

Medivir
Protocol: MIV-711-202

Final 1.0
16 January 2018

12. Figures

TLF Number	Title
Figure 14.2.1.1	Estimated Mean \pm 95% CI for MRI of Bone Area by Week and Group, ITT Population
Figure 14.2.1.2	Estimated Mean \pm 95% CI for MRI of Cartilage Thickness by Week and Group, ITT Population
Figure 14.2.1.3	Estimated Mean \pm 95% CI for MRI of Total BML Volume by Week and Group, ITT Population
Figure 14.2.1.4	Estimated change from Visit 2 MIV-711-201 \pm 95% for MRI of Bone Area by Week and Group, ITT Population
Figure 14.2.1.5	Estimated change from Visit 2 MIV-711-201 \pm 95% for Cartilage Thickness by by Week and Group, ITT Population
Figure 14.2.1.6	Estimated change from Visit 2 MIV-711-201 \pm 95% for MRI of Total BML Volume by Week and Group, ITT Population
Figure 14.2.1.7	Estimated change from Visit 2 MIV-711-201 \pm 95% for MRI of Bone Area by Week and Group, PPS Population
Figure 14.2.1.8	Estimated change from Visit 2 MIV-711-201 \pm 95% for Cartilage Thickness by Week and Group, PPS Population
Figure 14.2.1.9	Estimated change from Visit 2 MIV-711-201 \pm 95% for MRI of Total BML Volume by Week and Group, PPS Population
Figure 14.2.3.1	Estimated Mean \pm 95% CI for NRS Items by Week and Group, ITT Population

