Figure 14.2.3.2	Estimated change from visit 2 MIV-711-201 \pm 95% CI for NRS Items by Week and Group, ITT Population
Figure 14.2.4.1	Estimated Mean \pm 95% CI for WOMAC Items by Week and Group, ITT Population
Figure 14.2.4.2	Estimated change from visit 2 MIV-711-201 \pm 95% CI for WOMAC Items by Week and Group, ITT Population
Figure 14.2.4.3	Estimated Mean \pm 95% CI for Normalized WOMAC Scores by Week and Group, ITT Population
Figure 14.2.4.4	Estimated change from visit 2 MIV-711-201 \pm 95% CI for Normalized WOMAC Scores by Week and Group, ITT Population
Figure 14.2.5.1	Estimated Mean \pm 95% CI for NRS E-Diary by Week and Group, ITT Population
Figure 14.2.5.2	Estimated change from visit 2 MIV-711-201 \pm 95% CI for NRS e-diary by Week and Group, ITT Population
Figure 14.2.5.3	Estimated Mean \pm 95% CI for Percentage Score E-Diary Analgesic Usage by Week and Group, ITT Population
Figure 14.2.5.4	Estimated change from visit 2 MIV-711-201 \pm 95% CI for Percentage Scores of E-Diary Analgesic Usage by Week and Group, ITT Population
Figure 14.2.6.1	Estimated Mean \pm 95% CI for Efficacy Biomarkers by Week and Group, ITT Population
Figure 14.2.6.2	Box Plots of Time Integrated Concentrations and their Z-Scores for Efficacy Biomarkers from Serum and Urine Samples by Group, ITT Population

PAREXEL International Statistical Analysis Plan

Medivir
Protocol: MIV-711-202

Final 1.0
16 January 2018

Figure 14.2.7.1	Mean \pm 95% CI Profiles of Observed Systolic Blood Pressure by Week and Group, SAF Population
Figure 14.2.7.2	Mean \pm 95% CI Profiles of Observed Heart Rate by Week and Group, SAF Population
Figure 14.2.8.1	Mean (95% CI) Profiles of Observed QTcB Interval by Week and Group, SAF Population
Figure 14.2.8.2	Mean (95% CI) Profiles of Observed QTcF Interval by Week and Group, SAF Population

PAREXEL International Statistical Analysis Plan

Medivir
Protocol: MIV-711-202

Final 1.0
16 January 2018

13. Listings

TLF Number	Title
Listing 16.2.1.1	Patient Disposition
Listing 16.2.1.2	Patients Excluded from Analysis Populations
Listing 16.2.1.3	Enrolled Patients Who Did Not Meet All Eligibility Criteria
Listing 16.2.1.4	Exclusion Tests
Listing 16.2.2.1	Protocol Deviations
Listing 16.2.4.1	Demographics
Listing 16.2.4.2	Medical History
Listing 16.2.5.1	Prior and Concomitant Medications
Listing 16.2.5.2	Dose Administration at Clinic Visits
Listing 16.2.5.3	Dose Administration Compliance, ITT Population

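### SAP 8.1.1 specifies 90% limits in text and code, but its example table, all 8 model table shells and at least 16 model-based figure titles say 95%

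*SAP*

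**What the plan says.** SAP 8.1.1 describes a linear mixed model for the MRI endpoints and gives default SAS code containing "LSMEAN group*visit / diff CL ALPHA=0.1". The text after the code says that mean levels and changes from Visit 2 of MIV-711-201 will be estimated "together with the corresponding 90% confidence interval". Text and code therefore agree on 90%.

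The outputs for the same estimates say otherwise:

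- "Table 1 Example table of statistical analysis corresponding to Figure 1 and Figure 2", also in 8.1.1, heads its interval columns 95% CI.
- The eight shells for model results in Section 14 (Tables 14.2.1.7, 14.2.1.8, 14.2.1.9, 14.2.3.2, 14.2.4.3, 14.2.4.4, 14.2.6.2 and 14.2.7.3) do the same, for both mean level and change.
- The model-based figure titles in Section 12 say 95%. Examples are "95% CI for MRI of Bone Area by Week and Group, ITT Population" (Figure 14.2.1.1), "95% CI for NRS Items by Week and Group, ITT Population" (Figures 14.2.3.1-2) and "95% CI for Efficacy Biomarkers by Week and Group, ITT Population" (Figure 14.2.6.1). Figures 14.2.1.4-9 give the level without the letters CI, as in "95% for MRI of Bone Area by Week and Group, ITT Population".

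The model is used beyond MRI in the ITT set. Sections 8.3.1.1, 8.3.3.1, 8.3.7.2 and 8.3.8.1 apply it to NRS, WOMAC, e-diary NRS and the two biomarkers. For MRI, Section 8.1 adds a second population: "The analyses of the imorphics MRI will be made on the ITT group and on the PPS population".

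On site, the text of 8.1.1 calls for random effects of site and patient. The code has `RANDOM site`, but CLASS lists only patient, visit, group and baseline analgesic use.

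**The concern.** The shells are working specifications. SAP Section 1 says the plan includes the programming specifications for tables, listings and figures, and Section 10 refers to the shells for output requirements. A programmer who follows the code and the shells together will print 90% limits under a 95% heading.

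The model shells have no p-value column, so the interval is the only inferential quantity a reader sees. For Group A, the within-patient MRI change from Visit 2 of MIV-711-201 is the main readout for the secondary objectives. Section 6 applies no multiplicity adjustment. Limits narrower than their label would make these results look more precise than they are.

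**Working it through.** **1. Level set by the code.** Level = 100 × (1 − ALPHA) = 100 × (1 − 0.1) = 90%. This reproduces the figure in the 8.1.1 text. A 95% level needs ALPHA = 0.05.

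**2. Outputs labelled 95%.**

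| Output | Labelled 95% |
|---|---|
| Example Table 1 in 8.1.1 | 1 of 1 |
| Model table shells | 8 of 8 |
| Figures the text clearly assigns to the model: 14.2.1.1-9, 14.2.3.1-2, 14.2.4.3-4, 14.2.5.1-2, 14.2.6.1 | 9 + 2 + 2 + 2 + 1 = 16 |

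Four more figures have titles describing estimated values and say 95%. The text models only one WOMAC item (Figures 14.2.4.1-2) and does not model percentage analgesic use (14.2.5.3-4), so they are not in the 16; with them the total is 20. Figures 14.2.7.1-2 and 14.2.8.1-2 also say 95% but plot observed means, so they are not counted.

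**3. Width.** Ratio of 90% to 95% half-width = quantile at 0.95 ÷ quantile at 0.975. The degrees of freedom are assumed, because the documents do not fix them.

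| Reference | 90% | 95% | Ratio |
|---|---|---|---|
| Normal | 1.645 | 1.960 | 0.839 |
| t, 20 df | 1.725 | 2.086 | 0.827 |
| t, 40 df | 1.684 | 2.021 | 0.833 |
| t, 80 df | 1.664 | 1.990 | 0.836 |

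The printed limits would be 16% to 17% narrower than labelled. Correct 95% half-widths would be 1.19 (1/0.839) to 1.21 (1/0.827) times as wide. In the normal case, an estimate between 1.645 and 1.960 standard errors from zero (two-sided p from 0.05 to 0.10) excludes zero at 90% but not at 95%.

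**4. Number of intervals.** Change intervals = parameters × 2 groups × rows after Visit 2 of MIV-711-201:

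- bone area 1×2×2 = 4
- cartilage 2×2×2 = 8
- BML volume 1×2×2 = 4
- NRS 5×2×5 = 50
- normalized WOMAC 3×2×5 = 30
- WOMAC walking item 1×2×5 = 10
- e-diary NRS 3×2×4 = 24
- biomarkers 2×2×6 = 24

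The total is 154. Mean-level intervals, with the Visit 2 row included, are 6 + 12 + 6 + 60 + 36 + 12 + 30 + 28 = 190. These counts leave out the MIV-711-201 Visit 5 row in the e-diary shell, because the schedule in SAP 4.1 has no e-diary at that visit. With the row as printed they are 154 + 6 = 160 and 190 + 6 = 196.

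Of the 154 change intervals, 154 × 0.10 = 15.4 would be expected to miss the true value, against 154 × 0.05 = 7.7 at the labelled level.

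**5. Site.** A random effect not listed in CLASS is treated by PROC MIXED as continuous. If site is numeric, the code fits one random slope on the site number, and the mean-level estimates and their limits can then depend on how sites are numbered. If site is character, the step stops with an error. Neither is the per-site effect in the text. The documents do not give the variable type, site coding or site variance, so no size can be stated. The patient effect is not a further problem: `REPEATED` with patient as subject and an unstructured covariance covers within-patient correlation.

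**The case against.** The strongest reply is that little depends on these intervals. Protocol 9.2.1 says the study is not powered for confirmatory analysis, and SAP Section 3 disclaims a formal statistical analysis. The primary safety endpoint is descriptive, and no success rule uses the limits. That stands, and it limits the severity. The harm is a misleading label on secondary and exploratory results, with no effect on a study decision.

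A second reply is that the harm is conditional. If the programmer notices the conflict, or sets ALPHA from the shells, nothing is mislabelled. That is also true, but the plan would then have been settled by whoever wrote the program. The 15.4 against 7.7 comparison only restates 10% against 5% over a hand count. It shows scale and is not separate evidence.

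On site, the code is a template with no dataset named, the text makes the intention plain, and the listed fallbacks already allow the site term to be dropped. A character variable would produce an error that is found at once. This is fair, and it is why the site point is secondary. It does not remove the mismatch between the code and the model described.

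**Conclusion.** The point holds and should be fixed. The 90% and 95% specifications contradict each other, nothing in either document resolves them, and neither level is wrong in itself. If the default code is run and the headings are kept, limits labelled 95% have 90% nominal coverage and are about 16% to 17% too narrow (normal approximation, or t with 20 to 80 assumed df). All modelled secondary and exploratory endpoints are affected; the primary safety analysis is not.

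The site omission is real but minor. With a numeric site variable it touches only the mean-level estimates and their limits; within-patient changes from Visit 2 are essentially unaffected.

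**What to change.** Choose one confidence level and use it throughout: the 8.1.1 text, the ALPHA option, example Table 1, the eight model table shells and the model-based figure titles. Either set ALPHA=0.05 and change the text to 95%, or keep ALPHA=0.1 and relabel every model-based heading 90%.

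State in 8.3.3.1 and 8.3.7.2 whether Figures 14.2.4.1-2 and 14.2.5.3-4 come from this model, so that their limits follow the same rule. Add site to CLASS.

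The cost is one option value and one number in the text (or heading edits only), a clarifying sentence in each of the two sections, and one word in the code. No new data or analyses are needed. It should be settled before output is produced.

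### On non-convergence, SAP 8.1.1 lists compound symmetry before removal of the site effect; reversing the order would better protect the 52-week change intervals, at little cost

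*SAP*

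**What the plan says.** The default model in SAP 8.1.1 has fixed effects for group, visit, their interaction and baseline analgesic use, a random site effect, and the within-patient structure "REPEATED visit / SUBJECT=patient TYPE=UN". Intervals are set by "LSMEAN group*visit / diff CL ALPHA=0.1", which is the 90% level.

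The fallback rule is "In case of convergence issues, a reduced model will be used to achieve convergence". It continues: "The first two model reductions that will be considered are the following", followed by a numbered list:

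1. "Simplify the covariance structure by using a compound symmetry covariance structure instead of unstructured"
2. "Omit the random effect of site"

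No structure between unstructured (UN) and compound symmetry (CS) is named. The SAP does not say whether step 2 is applied on top of CS or with UN restored.

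Two kinds of estimate are reported: "The mean level and the change from visit 2 in study MIV-711-201 will be estimated for each population*visit combination". SAP 8.3.1.1, 8.3.3.1, 8.3.7.2 and 8.3.8.1 carry the same model to NRS, WOMAC, e-diary NRS and the two biomarkers.

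**The concern.** The secondary objectives for Group A (SAP 2.2) concern change over 52 weeks. Protocol 2.3 and 2.4 explain why: cartilage change is not expected to show at 6 months and needs about 12. The precision of the 52-week change is therefore worth protecting.

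A site intercept takes the same value at every visit of a patient, so it has almost no bearing on that precision. The within-patient covariance determines it. Read in its numbered order, the fallback gives up the covariance first and the site term second. Site is also a plausible cause of convergence trouble, because its variance has to be estimated from at most five centres (Protocol 5.4).

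**Working it through.** **Inputs from the documents.** Nominal level 90% (SAP 8.1.1 text and code). Three MRI time points: Visits 2 and 8 of MIV-711-201 and Visit 5 of MIV-711-202 (Protocol 7.2). Six NRS/WOMAC visits and seven biomarker visits (shells of Tables 14.2.3.2, 14.2.4.3 and 14.2.7.3). Expected 50–80 patients (SAP 3.2). Up to five sites (Protocol 5.4). No SD, correlation or site variance is given, so every covariance below is an assumption.

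**The plan's own figure.** ALPHA=0.1 gives z = 1.645, and 2Φ(1.645) − 1 = 0.90.

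**Covariance parameters.** UN with k visits has k(k+1)/2: 6 for k = 3, 21 for k = 6 and 28 for k = 7. CS has 2 in each case.

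**Effect of CS on change.** Let D(i,j) be the true variance of the change between visits i and j. With complete data, CS sets every such variance to the mean of all the D(i,j). For three visits:

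SE ratio (CS / correct) at week 52 = √[mean(D12, D23, D13) / D13]; large-sample coverage = 2Φ(1.645 × ratio) − 1.

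*Worked case.* Assume equal variances and correlations of 0.80 over 26 weeks and 0.65 over 52 weeks.
- CS correlation = (0.80 + 0.80 + 0.65)/3 = 0.75.
- Week 52: √(0.25/0.35) = 0.845. Coverage of the 90% interval is 2Φ(1.390) − 1 = 0.836. At the 95% level printed in the table shells it would be 0.902.
- Week 26: √(0.25/0.20) = 1.118, so the standard error is 12% too large.

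*Range of assumptions, three visits:*

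| Assumed structure | Week-52 SE ratio | Coverage of 90% interval |
|---|---|---|
| CS true | 1.00 | 90% |
| Random walk, variance per 26 weeks 0.5–2 × error variance | 0.94–0.88 | 88–85% |
| Random slope, variance 0.25–2 × error variance | 0.91–0.78 | 87–80% |
| AR(1), 0.9 per 26 weeks | 0.83 | 83% |
| Pure random walk (limit) | 0.82 | 82% |
| Pure random slope (limit) | 0.71 | 76% |

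Except where CS is true, the 26-week standard error errs the other way, by 3% to 41%.

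*Six NRS/WOMAC visits, same method.* Pure exponential decay at 0.6–0.8 per 13 weeks gives 0.81–0.74. A stable patient component of 0.4–0.6 of the variance, a decaying part of 0.3–0.1 (0.8 per 13 weeks) and 0.3 noise gives 0.91–0.96.

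**Effect of dropping site.** REML fits to simulated data: 40 + 20 patients, 5 sites, 10% missing at Visit 5, 120 runs per setting, two covariances (AR(1) 0.9; random slope variance equal to error variance) and three site variances, on a scale where between-patient variance is about 1. The analgesic covariate was left out. Standard errors are for Group A, relative to UN with site.

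| Model | SE of 52-week change | SE of week-52 mean level |
|---|---|---|
| UN, no site; true site variance 0 | 1.00 | 0.95–0.96 |
| UN, no site; 0.05 | 1.00 | 0.88–0.89 |
| UN, no site; 0.2 | 1.00 | 0.74–0.75 |
| CS with site, all settings | 0.82–0.84 | 0.96–1.00 |

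Under CS, then dropping site made no further difference to the change. With UN and site, the site variance was estimated at about zero in 58–66% of runs when the true value was 0, 35–37% at 0.05 and 12% at 0.2. Coverage from 120 runs carries about 3 points of Monte Carlo error. Separate three-visit runs without a site term (6,000 each) put week-52 coverage at 0.82–0.88 under CS and about 0.90 under UN.

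**The case against.** A reader might infer that the listed order gains nothing. The documents do not support that. Mean levels are reported with intervals alongside the changes, and site does not cancel from a mean level: CS with site keeps those standard errors at 0.96–1.00, while dropping site shrinks them. CS also cuts 21 or 28 parameters to 2 for NRS/WOMAC and the biomarkers. With 50–80 patients, UN itself may be what fails there. A site variance estimated at zero simply reproduces the no-site model and does not prove that site causes the failure. These objections stand.

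A reader might also infer that CS yields a wrong standard error. That is conditional: with no correlations given, the error could be nil. Nor is a strict sequence stated. It comes from the numbering, which is the natural reading but not an explicit rule.

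The 52-week change is not central for both groups. SAP 8 sets Group B's efficacy baseline at Visit 8 of MIV-711-201, so its on-treatment change spans 26 weeks, where CS would tend to be conservative.

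Lastly, little depends on it. The rule applies only on non-convergence, Protocol 9.2.1 disclaims confirmatory power, and Tables 14.2.1.1–14.2.1.6 summarise observed change without the model.

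None of this explains going straight from UN to CS. For the three-visit MRI model the convergence argument for CS first is weak: UN has six parameters and, with complete data and no site term, a closed-form fit.

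**Conclusion.** The point holds as a minor improvement. For change from Visit 2, dropping site first left the standard error unchanged in all six simulated settings. CS first can make the 52-week interval too narrow if correlation fades: a ratio of 1.00 if CS is true, about 0.96–0.83 under a patient component with decay, random walks or AR(1), and 0.71 at the pure-slope limit. At assumed correlations of 0.80 and 0.65 the ratio is 0.845, with about 84% coverage of a nominal 90% interval. These sizes rest on assumed covariances.

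The price of site-first is paid in the mean-level intervals, whose standard errors were about 4–26% smaller. The low end is the case with no true site variance, where nothing real is lost. Because the stated objectives concern change over 52 weeks, the trade favours site-first.

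**What to change.** Rewrite the fallback list in SAP 8.1.1:

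1. Drop the random site effect and keep TYPE=UN.
2. If UN still fails, as is plausible for the six- and seven-visit models, try structures with unequal variances and non-constant correlation: heterogeneous Toeplitz, ARH(1), or a time-based spatial structure. The visits are unevenly spaced and Group B changes treatment midway, so the choice needs thought by endpoint.
3. Use CS last, with a robust-standard-error sensitivity analysis that uses a compatible degrees-of-freedom method in place of DDFM=KR.

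State whether the steps are cumulative. Footnote any mean-level table or figure produced without site, saying that its intervals ignore site clustering.

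In the same edit, add site to the statement "CLASS patient visit group baseline_conmed_pain_use". As coded, a numeric site identifier would enter as a continuous random coefficient, which could itself cause convergence trouble.

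The cost is a few lines of SAP text, some extra programming for steps 2 and 3, and the loss of site clustering in mean-level intervals whenever step 1 is used. No data collection changes.

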The analysis of data from the proposed study will not be based on a formal statistical analysis since the primary endpoint constitutes safety and tolerability. All efficacy parameters measured in Study MIV-711-201 will also be measured in the proposed study. However, the important difference is that any comparisons will be made from baselines within but not between Study Population A and B. In contrast, in Study MIV-711-201, comparisons will be made between treatment groups with a formally powered analysis regarding the primary endpoint.

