2.5 Exploratory Objectives Study Group B

All of the above noted secondary and exploratory parameters described in Section 2.2 and Section 2.4 for study group A, are considered as exploratory objectives in study group B and will be evaluated over 26 weeks on 200 mg MIV-711 succeeding 26 weeks on Placebo.

3. Study Design

This study is a 6-month open-label one-arm extension study evaluating safety and tolerability as well as the efficacy of 200 mg MIV-711 q.d. in two separate patient populations denoted as study Group A and Group B.

Study Group A patients will be recruited from Study MIV-711-201 who were treated with 200 mg MIV-711 q.d. and whose symptoms did not clinically significantly deteriorate as defined by an increase in the numeric rating scale (NRS) of ≤ 2 compared to Baseline. Patients eligible for Study Group A will be offered 6 months' extended treatment, primarily evaluating longer term safety and tolerability. The total treatment duration of 52 weeks also allows a more suitable treatment length for the exploratory study of any structural effects of MIV-711 on joint cartilage thickness.

[figure not shown]
A further rationale of this study is to explore the treatment effect in a group of OA patients that have confirmed symptom progression over the last 6 months (Study Group B). Study Group B will be recruited from patients receiving placebo in Study MIV-711-201 who experienced a clinical worsening as defined by an increase in NRS of ≥ 2 versus Baseline. Patients eligible for Study Group B will be offered 200 mg MIV-711 q.d. for the next 26 weeks. In addition to offering the treatment to appropriate patients, this also enables the assessment of the effects of MIV-711 based on MRI imaging, symptoms and biomarkers in patients with progressing symptoms and, as such, has the potential to provide valuable information for future patient selection in OA trials. Similar to Study MIV-711-201, the joint structural endpoint of choice over 6 months treatment constitutes MRI joint bone surface measurement. All analyses, with the exception of safety and tolerability, will be conducted as exploratory with regards to Study Group B.

The analysis of data from this study will not be based on a formal statistical analysis since the primary endpoint constitutes safety and tolerability.

PAREXEL International Statistical Analysis Plan

Medivir
Protocol: MIV-711-202

Final 1.0
16 January 2018

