7.9 Dose Administration

Information collected per the dose administration CRF will be listed including patient number, visit, date and time of administration, number of capsules dispensed and number of capsules returned.

The number and percentage of patients who received IMP will be summarized for each on site visit. Descriptive statistics will be used to summarize drug accountability as the number of capsules returned for each on site study visit by treatment.

Compliance will be derived as the number of days patient were exposed to IMP. 100% compliance will be considered for dosing during the period Visit 2 to Visit 5. The number of capsules used will be derived as the number of capsules dispensed minus the number of capsules returned. Subjects with less than 100% compliance will be identified among those who have results for “Reason not all unused Capsules returned”. The compliance will not be calculated for withdrawn patients, as the date of the last IMP dose taken is not captured in the database.

8. Pharmacodynamic Analysis – Efficacy

The baseline will be the last valid assessment prior to first dose of 200 mg MIV-711, i.e. the baseline visit is defined as

- Visit 2 in study MIV-711-201 for study group A
- Visit 8 in study MIV-711-201 for study group B

The exception is for the biomarkers in study group B, where the baseline visit is defined as visit 2 in the present study (MIV-711-202).

The change from baseline for visit X will be calculated as the (visit X – baseline visit) difference in observed values. Note that the change from baseline will be calculated for all visits in study MIV-711-201 and study MIV-711-202 where the actual endpoint has

PAREXEL International Statistical Analysis Plan

Medivir
Protocol: MIV-711-202

Final 1.0
16 January 2018

been observed, i.e. not only for visits in study MIV-711-202 succeeding the baseline visit.

All efficacy analyses will be made on the ITT population if not stated otherwise.

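### For Group B, the SAP's MRI model tables report change only from 201 Visit 2, so the final row mixes the placebo and drug periods and cannot separate a drug effect from natural progression

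*SAP*

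**What the plan says.** SAP 8.1.1 fits one linear mixed model to the MRI scores of both groups across both studies. Its reported quantities are fixed: "The mean level and the change from visit 2 in study MIV-711-201 will be estimated for each population*visit combination", "together with the corresponding 90% confidence interval". The column heading in the example table is "Estimated Change from Visit 2, Study MIV-711-201". The shells for Tables 14.2.1.7 to 14.2.1.9 have the same layout, and Figures 14.2.1.4 to 14.2.1.9 plot the same change. The code requests "LSMEAN group*visit / diff CL ALPHA=0.1" and has no ESTIMATE or CONTRAST statement.

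Elsewhere the SAP frames Group B differently. Under 2.5 its MRI parameters "will be evaluated over 26 weeks on 200 mg MIV-711 succeeding 26 weeks on Placebo". Section 8 sets the efficacy baseline at "Visit 8 in study MIV-711-201 for study group B", and Protocol 9.5.3.1 agrees. SAP section 3 says of treating this group that "this also enables the assessment of the effects of MIV-711 based on MRI imaging, symptoms and biomarkers in patients with progressing symptoms". Protocol 2.4 restricts comparisons: "any comparisons will be made from baselines within but not between Study Population A and B".

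**The concern.** The model output for Group B answers a different question from the one the SAP sets. Of its two change rows, the first (to 201 Visit 8) is a pure placebo change. The second (to 202 Visit 5) is placebo plus drug. Neither isolates the drug period.

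Zero is also a poor reference for either row. Protocol 2.3 describes structural progression that no available treatment counteracts. In that setting, absence of a drug effect means that the knee changes on drug as it did on placebo; it does not mean no change. An inactive drug then leaves a Visit 2 to Visit 5 change that grows with progression, and a drug that reversed the placebo-period change would bring it back to zero.

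Protocol 2.3 presents Group B as a first opportunity to explore a candidate disease-modifying drug in patients with verified symptom progression. The design supplies what is needed for a within-patient look, with scans at 201 Visit 2, 201 Visit 8 and 202 Visit 5. The planned tables do not use it.

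**Working it through.** The documents give no effect size, SD or power for this analysis, so there is no plan figure to reproduce. The code's ALPHA=0.1 does match the 90% interval in the text of 8.1.1. The example table, shells and figure titles say 95%, which needs reconciling separately.

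**Inputs.** From the documents: three MRI visits; a 90% interval; 50 to 80 patients in total. Assumed, because the documents do not give them: Group B size n = 8, 15 or 25; mean untreated change m = 0.2, 0.4 or 0.6 per 26 weeks, in units of the SD of one 26-week change; share r = 0.3 to 0.8 of that variance due to measurement error; patient-specific linear progression; complete data; inactive drug.

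**Model.** Patient slope has mean m and variance 1 − r. Each scan has error variance r/2, so one 26-week change has variance (1 − r) + r = 1.

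- V5 − V2: mean 2m, variance 4(1 − r) + r
- V5 − V8: mean m, variance 1
- D = (V5 − V8) − (V8 − V2) = V5 − 2·V8 + V2: mean 0, variance (1 + 4 + 1)·r/2 = 3r

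The chance that the interval excludes 0 is P(|T| > t₀.₉₅,ₙ₋₁), with T noncentral t on n − 1 df and δ = mean × √n / SD.

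**Worked case, n = 15, m = 0.4** (critical value 1.761):

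- V5 − V2, r = 0.3: variance 2.8 + 0.3 = 3.1; δ = 0.8 × 3.873 / 1.761 = 1.76; 51%
- V5 − V2, r = 0.8: variance 0.8 + 0.8 = 1.6; δ = 0.8 × 3.873 / 1.265 = 2.45; 75%
- V5 − V8: δ = 0.4 × 3.873 = 1.55; 43%
- D: δ = 0; 10%

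**Range over all m and r, inactive drug:**

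| n | V5 − V2 | V5 − V8 | D |
|---|---|---|---|
| 8 | 16–78% | 14–46% | 10% |
| 15 | 22–97% | 19–71% | 10% |
| 25 | 30–99.8% | 26–90% | 10% |

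Simulation of 3000 trials per setting agrees to within about two percentage points. The 10% for D holds by construction, since the model has linear progression and no selection. The 10 ± 5 day gap before 202 dosing makes the second interval about 192 days against 182; in a simpler model with SD 1 for every change, this raises D's rate to at most 10.3%.

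**Direction.** In that same simpler model, with n = 20 and m = 0.5, V5 − V2 excludes zero in over 99% of trials if the drug is inactive, 70% if it fully arrests progression, and 10% if it exactly reverses the placebo-period change. The better the drug, the less often this interval excludes zero.

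**Precision of D.** If the drug fully arrests progression, D has mean −m and variance (1 − r) + 3r. At n = 15 and m = 0.4:

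- r = 0.3: variance 1.6, δ = 1.22 in size, 32%
- r = 0.8: variance 2.6, δ = 0.96 in size, 24%

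As measurement error comes to dominate (r near 1), D's variance approaches 3 times that of a single change.

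**The case against.** A reader might infer that the SAP tests a no-change hypothesis in Group B and would declare a drug effect when zero is excluded. The documents do not support that. Both disclaim a formal statistical analysis, Protocol 9.2.1 disclaims power for confirmatory analyses, Protocol 9.5.3.2 keeps exploratory analyses descriptive, and 8.1.1 says the model is for describing the response over both studies. There is no decision rule. What remains is how a plotted interval around a change will be read.

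A reader might also infer that the drug period is never estimated. It is. The code's pairwise differences include V5 − V8 with an interval. SAP sections 6 and 8 compute change for visits before baseline as well, and the descriptive shells (Tables 14.2.1.1 to 14.2.1.3) leave Group B's change cell empty at Visit 8 and fill it at Visits 2 and 5. Both period changes thus appear with n, mean and SD. The point estimate of D even follows from the planned rows as (V5 − V2) − 2(V8 − V2). Its standard error needs the covariance of the two changes, which those tables do not carry.

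The strongest objection is to calling D the drug effect, and it stands. Group B was selected on pain worsening during the placebo period, and the protocol abstract links subchondral bone pathology to symptoms. If structural change in that period was partly transient and correlated with the selected pain rise, D would favour an inactive drug. As an illustration on assumed values (Group B as the top 20% on pain change, correlation 0.2 to 0.4, m = 0.4, n = 15), D excludes zero in 14–21% to 27–50% of trials, almost always in the drug's favour. Protocol 2.3 also does not expect cartilage change to be visible on MRI within 6 months.

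**Conclusion.** The point holds as a mismatch between the Group B question and the tabulated model output. The 202 Visit 5 row pools placebo and drug time, contrary to the SAP's own Visit 8 baseline, and read against zero it cannot separate drug effect from progression. Resetting the reference to Visit 8 removes the pooling but not the second problem.

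The size is not determined by the documents. Under the assumptions above, an inactive drug yields an interval excluding zero in about 15% to over 99% of trials for V5 − V2 and 14% to 90% for V5 − V8, against a nominal 10%. It would be wrong to say that progression will exclude zero; that depends on an unstated group size and progression rate.

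What is missing is a model table row for the drug period and any interval for the difference between periods. That difference is worth showing as an exploratory within-patient contrast. It does not support the label of drug effect. The primary safety analysis is unaffected.

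**What to change.** In SAP 8.1.1 and Tables 14.2.1.7 to 14.2.1.9, add for Group B, with intervals from the existing fit:

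1. placebo-period change, V8:201 − V2:201;
2. drug-period change, V5:202 − V8:201;
3. their difference, titled *exploratory within-patient period contrast*.

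Do not name row 3 the estimate of drug effect. Label every single-period and 52-week change, Group A's included, *change over time, not drug effect*.

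Footnote row 3: it assumes linear untreated progression; it is imprecise (up to 3 times the variance of a single change when measurement error dominates); and it may be biased in the drug's favour, because Group B was selected on placebo-period pain worsening, which may correlate with bone and BML change. For the cartilage rows, add that the protocol does not expect change to be apparent over 6 months.

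Do not carry row 3 over to NRS pain, which 8.3.1.1 runs through the same model, because the placebo-period rise in that score was the selection criterion.

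Correct the MRI shell footnotes that give Visit 2 as the baseline for both groups so that they agree with section 8. Where a column is deliberately referenced to 201 Visit 2, call that the reference visit.

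The cost is ESTIMATE statements for three Group B contrasts, a few table rows and some footnotes. No new scans or data are needed. The contrast compares Group B only with itself, so the protocol's bar on comparing A with B is respected.
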